
 To assess the safety and tolerability of orally administered VH4524184 	
 Incidence of adverse events (AEs), severity of AEs and proportion of participants who discontinue treatment due to AEs Change from baseline and maximum toxicity grade increase from baseline for liver panel laboratory parameter (Alanine Transaminase (ALT), Aspartate aminotransferase (AST), total bilirubin, direct bilirubin, alkaline phosphatase, albumin and total protein)

 To characterize the pharmacokinetic profile of orally administered VH4524184 	As data permits, PK measures that include: 
 Maximum observed plasma drug concentration (Cmax), Time to maximum observed plasma drug concentration (tmax), Concentration on Day 10

 To evaluate any relationship between VH4524184 exposure and change in plasma HIV-1 RNA 	
 Correlation of VH4524184 PK parameters with maximum plasma HIV-1 RNA change from baseline through Day 10

 To assess the occurrence of emergent genotypic or phenotypic resistance after 10 days of monotherapy with VH4524184 	
 Genotypic and phenotypic data from baseline (Day 1) and Day 10 will be compared for amino acid substitutions and VH4524184 fold change IC50.

 To assess the immunologic effects of VH4524184 when administered over 10 days in participants living with HIV 	
 Change from baseline in CD4+ T-cell count to Day 10
Tertiary	

 To further assess the safety and tolerability of orally administered VH4524184 	
 Post baseline values and changes over time of vital signs, electrocardiogram (ECG) parameters and suicidality scores. Absolute values, change from baseline and maximum toxicity grade increase from baseline for hematology, coagulation and remaining chemistry panels

Overall Design:

This is a Phase 2a POC, multi-center, randomized, double-blind (sponsor unblinded), placebo-controlled, adaptive clinical study to evaluate the antiviral effect, safety, tolerability and PK/PD of orally administered VH4524184 over 10 days in up to approximately 28 antiretroviral therapy (ART) naive adults with HIV-1 and detectable viremia.

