3. OBJECTIVES, ENDPOINTS AND ESTIMANDS

Table 3 Objectives and Endpoints

Objective(s)	Endpoint(s)
Primary	

 To evaluate the antiviral activity of orally administered VH4524184 in TN participants with HIV-1 during 10 days of monotherapy 	
 Maximum change from baseline (Day 1) in plasma HIV-1 RNA through Day 10.
Secondary	

 To assess the safety and tolerability of orally administered VH4524184 	
 Incidence of AEs, severity of AEs and proportion of participants who discontinue treatment due to AEs Change from baseline and maximum toxicity grade increase from baseline for liver panel laboratory parameter (ALT, AST, total bilirubin, direct bilirubin, alkaline phosphatase, albumin and total protein)

 To characterize the pharmacokinetic profile of orally administered VH4524184 	As data permits, PK measures that include: 
 Cmax, tmax Concentration on Day 10

 To evaluate any relationship between VH4524184 exposure and change in plasma HIV-1 RNA 	
 Correlation of VH4524184 PK parameters with maximum plasma HIV-1 RNA change from baseline through Day 10

 To assess the occurrence of emergent genotypic or phenotypic resistance after 10 days of monotherapy with VH4524184 	
 Genotypic and phenotypic data from baseline (Day 1) and Day 10 will be compared for amino acid substitutions and VH4524184 fold change IC50.

 To assess the immunologic effects of VH4524184 when administered over 10 days in participants living with HIV 	
 Change from baseline in CD4+ T-cell count to Day 10
Tertiary	

 To further assess the safety and tolerability of orally administered VH4524184 	
 Post baseline values and changes over time of vital signs, ECG parameters and suicidality scores. Absolute values, change from baseline and maximum toxicity grade increase from baseline for hematology, coagulation and remaining chemistry panels

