9.3.3.1 Safety analyses

All safety analyses will be performed on the Safety analysis set. Safety data will be presented in tabular format and summarized descriptively according to GSK's IDSL.

The number and proportion of participants with AEs will be tabulated overall and by severity grade, by study intervention and dose level. The number and proportion of participants with AEs leading to discontinuation of study intervention will also be tabulated by dose level. In AE tabulations, each participant's AE will be counted once under the maximum severity. AEs will be tabulated using MedDRA preferred terms. AEs will be tabulated for the monotherapy period and overall (i.e., monotherapy period plus SOC period) separately.

For liver panel laboratory parameters, summary statistics of change from baseline values by visit will be presented by study intervention and dose level. Number and percentage of participants with maximum toxicity grade increase from baseline for liver panel parameters will be presented by study intervention and dose level; this will be done separately for the monotherapy period and overall (i.e., monotherapy period plus SOC).

No imputation will be performed for missed assessments while participants are on study or after study withdrawal.

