10.2 Appendix 2: Clinical laboratory tests

- The clinical safety laboratory tests detailed in [Table 9](#) will be performed by the central laboratory.
- Local laboratory results are only required in the event that the central laboratory results are not available in time for either study intervention administration and/or response evaluation. If a local sample is required, it is important that the sample for central analysis is obtained at the same time. Additionally, if the local laboratory results are used to make either a study intervention decision or response evaluation, the results must be recorded.
- Protocol-specific requirements for inclusion or exclusion of participants are detailed in Section [5](#) of the protocol.
- Additional tests may be performed at any time during the study as determined necessary by the investigator or required by local regulations.
- Investigators must document their review of each laboratory safety report.

Table 9 Protocol-required safety laboratory tests

Laboratory Tests	Parameters	
Hematology	
 ▪ Platelet count 	
	
 ▪ Red blood cell (RBC) count 	
	
 ▪ RBC indices 	
 ▪ Mean corpuscular volume (MCV) ▪ Mean corpuscular hemoglobin (MCH) ▪ %Reticulocytes
	
 ▪ WBC count with differential: 	
 ▪ Neutrophils ▪ Lymphocytes ▪ Monocytes ▪ Eosinophils ▪ Basophils
	
 ▪ Hemoglobin 	
	
 ▪ Hematocrit 	

Laboratory Tests	Parameters	
Clinical chemistry¹	
 ▪ Blood urea nitrogen (BUN)/Urea ▪ Potassium ▪ Creatinine² ▪ Sodium ▪ Bicarbonate ▪ Magnesium ▪ Phosphate ▪ Calcium ▪ Glucose (fasting) ▪ Creatine phosphokinase (CPK)⁵ 	
 ▪ Aspartate aminotransferase (AST)/serum glutamic-oxaloacetic transaminase (SGOT) ▪ Alanine aminotransferase (ALT)/serum glutamic-pyruvic transaminase (SGPT) ▪ Alkaline phosphatase³ ▪ Total bilirubin ▪ Direct bilirubin⁴ ▪ Total protein ▪ Amylase
	
 ▪ Lipase (fasting) 	
 ▪ Fasting lipid panel (cholesterol, triglycerides, high-density lipoprotein [HDL], low-density lipoprotein [LDL])

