Coagulation	
 ▪ Prothrombin time (PT) ▪ Partial thromboplastin time (PTT) ▪ International normalized ratio (INR) 	
Routine urinalysis	
 ▪ Specific gravity ▪ pH, glucose, protein, blood, ketones, bilirubin, urobilinogen, nitrite, leukocyte esterase by dipstick ▪ Microscopic examination (if blood or protein is abnormal) 
 ▪ Epithelial cells ▪ Red Blood cells ▪ WBC ▪ Casts ▪ Crystals ▪ Culture (if positive: specify pathogen) 	

Laboratory Tests	Parameters
Other screening tests	
 ▪ Follicle stimulating hormone and estradiol (as needed in PONCBP only [See Section 10.4.1] Contraceptive and barrier guidance - Definitions) ▪ Highly sensitive (serum or urine) human chorionic gonadotropin (hCG) pregnancy test participants female at birth.[See Section 1.3, Schedule of Activities] ▪ Serum or urine alcohol, cotinine, and drug screen (to include at minimum: amphetamines, barbiturates, cocaine, opiates, cannabinoids and benzodiazepines) ▪ Serology [(HIV antibody 4th generation test, HBsAg, and HCV antibody Hepatitis B surface antibody (anti-HBs) and if indicated hepatitis B DNA (by PCR), and hepatitis C virus antibody)], with reflex to HCV RNA (by PCR) if positive. ▪ Syphilis positive rapid plasma reagin (RPR)

NOTES:

1. Details of liver chemistry stopping criteria and required actions and follow-up are given in Section 7.1.2 Liver Chemistry Stopping Criteria and Section 10.5: Liver Safety: Suggested Actions and Follow-up Assessments. All events of ALT $\geq 3 \times$ upper limit of normal (ULN) and total bilirubin $\geq 2 \times$ ULN ($> 35\%$ direct bilirubin) or ALT $\geq 3 \times$ ULN and international normalized ratio (INR) > 1.5 (if INR measured), which may indicate severe liver injury (possible Hy's law), must be reported to VH/GSK in 24 hours (excluding studies of hepatic impairment or cirrhosis).
2. To assess the kidney function, use the CKD-EPI equation (2021).
3. If alkaline phosphatase is elevated, consider fractionating.
4. Direct bilirubin will be reflexively performed for all total bilirubin values $> 1.5 \times$ ULN
5. Recommend repeat testing if CPK is elevated to ensure the result is transient or due to exercise. A history regarding use of drugs known to cause increase of CPK (such as statins), physical activity or exercise preceding the CPK evaluation should be obtained.

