	
 Viral hepatitis serology³ Syphilis screening Drugs of abuse screen, including alcohol Obtain INR and recheck with each liver chemistry assessment until the aminotransferases values show downward trend Obtain blood sample for pharmacokinetic (PK) analysis, documenting the date and time of the most recent VH4524184 dose⁴ Obtain serum CPK, LDH, GGT, GLDHand serum albumin Fractionate bilirubin, if total bilirubin \geq1.5xULN Obtain complete blood count with differential to assess eosinophilia Record the appearance or worsening of clinical symptoms of liver injury, or hypersensitivity, fatigue, decreased appetite, nausea, vomiting, abdominal pain, jaundice, fever or rash on the liver event form Record use of concomitant medications on the concomitant medications report form including acetaminophen, herbal remedies, recreational drugs, and other over-the-counter medications

Liver Chemistry Stopping Criteria	

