4.3.2.2. Liver panel laboratory analyses

Change from baseline values for liver panel laboratory parameters will be summarised by assessment visit. Visits up to Day 10 (inclusive) will exclude any liver panel values assessed under SoC, if SoC starts earlier for any reason, in line with the Estimand definition (section 1.1).

Laboratory toxicities will be graded according to the DAIDS Criteria Version 2.1. For liver panel lab tests that are gradable by DAIDS (e.g. ALT, AST), summary of worst-case grade increase from baseline grade will be provided. This summary will display the number and percentage of participants with a maximum post-baseline grade increase from their baseline grade. Also, maximum increase subtotals (i.e. max increase in grade to any grade between 1 and 4, max increase to grade 2-4 or max increase to grade 3-4) will be included. The grade increases are determined by comparing the baseline grade to the worst-case post-baseline grade (e.g., Increase to Grade 1, Increase to Grade 2 etc.) and maximum grade increase subtotals (e.g., Increase to Grades 1 to 4, Increase to Grades 2 to 4, Increase to Grades 3 to 4). The grading subtotals are determined by adding the counts for each worst-case grade change within the subtotal category, e.g., 'Increase to Grades 1 to 4' is a subtotal of all worst-case increases to Grade 1, to Grade 2, to Grade 3, and to Grade 4. Participants with missing baseline value are to be assumed to have a Grade 0 at baseline. The determination of the worst case during the post-baseline period takes into account both planned and unscheduled assessments. This summary will be produced while participants are under the monotherapy period, as well as overall (i.e. monotherapy + follow-up).

For lab tests that are not gradable by DAIDS, summaries of worst-case changes from baseline with respect to normal range will be generated. Decreases to low, changes to normal or no changes from baseline, and increases to high will be summarized for the worst-case post-baseline. If a subject has a decrease to low and an increase to high during the same time interval, then the subject is counted in both the "Decrease to Low" categories and the "Increase to High" categories.

Liver panel data for participants with at least one abnormal lab value will be included in the listing of chemistry laboratory parameters.

More details of all planned displays are provided in the OPS document.

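### Albumin is in the secondary liver-panel endpoint but not in Table 9, so the supplied text schedules no albumin test; whether direct bilirubin is routine also needs stating

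*Protocol*

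**What the plan says.** Protocol Table 3 defines the liver-panel endpoint on "ALT, AST, total bilirubin, direct bilirubin, alkaline phosphatase, albumin and total protein". The Protocol synopsis carries the same list ("total bilirubin, direct bilirubin, alkaline phosphatase, albumin and total protein"), and so does SAP 1.1. All three attach two measures to it: change from baseline, and maximum toxicity grade increase from baseline.

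For the first measure, Protocol 9.3.3.1 says that "summary statistics of change from baseline values by visit will be presented by study intervention and dose level". SAP 4.3.2.2 agrees: "Change from baseline values for liver panel laboratory parameters will be summarised by assessment visit". SAP 4.9 declares no change to the protocol's analyses, so albumin remains in the SAP endpoint.

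The tests themselves are set in Protocol 10.2, under the title "Table 9 Protocol-required safety laboratory tests". The chemistry rows of Tables 1 and 2 refer to that appendix, as does Protocol 8.3.4, which adds that testing also follows the laboratory manual. Table 9 does not contain albumin. It does contain direct bilirubin, with a footnote: "Direct bilirubin will be reflexively performed for all total bilirubin values" above 1.5 x ULN (Note 4).

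Serum albumin is otherwise requested only in Appendix 5, after a participant meets liver stopping criteria: "Obtain serum CPK, LDH, GGT, GLDHand serum albumin".

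**The concern.** An endpoint needs a matching line in the data-collection plan. Hepatotoxicity is one of the potential risks in Protocol 2.3.1, and the liver panel is a stated secondary safety endpoint. A site or laboratory that worked from Table 9 alone would not measure albumin at any scheduled visit. The albumin rows of the planned liver tables would then be empty, or would hold only results from participants who had a liver event.

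Direct bilirubin raises a different question. It is in the list, but the note attached to it describes a conditional test. If it is measured only on that condition, its change-from-baseline summary would describe participants selected for raised total bilirubin and not the treatment groups.

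**Working it through.** There is no plan figure to reproduce. The check sets the endpoint beside the test list and counts the draws.

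**1. Endpoint against Table 9**

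| Endpoint analyte | In Table 9? |
|---|---|
| ALT | yes |
| AST | yes |
| Total bilirubin | yes |
| Alkaline phosphatase | yes |
| Total protein | yes |
| Direct bilirubin | yes, with Note 4 (reflex above 1.5 x ULN) |
| Albumin | no |

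Six of the seven are named, and five of the seven carry no reflex note.

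**2. Scheduled chemistry draws per completing participant**
- Table 1: Screening and Days 1, 2, 4, 7 and 10, which is 6.
- Table 2: Days 17, 24, 31 and 38, which is 4.
- Total: 6 + 4 = 10. Without Screening and Day 1, 10 - 2 = 8 are post-baseline (4 in monotherapy, 4 in follow-up).
- Early-discontinuation and unscheduled samples are not counted.

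Albumin is specified at 0 of the 10.

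**3. What the SAP does with absent values**
- Change from baseline: SAP 4.1.2 leaves a missing baseline missing unless otherwise stated, and SAP 4.1.1 imputes nothing.
- Grade increase: SAP 4.3.2.2 does state otherwise. For gradable tests, a participant with no baseline is taken as Grade 0.
- Local results: under SAP 4.1.1 they go to listings and not to summaries.

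Without scheduled albumin, the first part of the endpoint has nothing to summarise. The second could receive only event-driven values. If albumin is gradable, those would be compared with an assumed Grade 0. The supplied text does not say which endpoint analytes are gradable beyond ALT and AST, which it gives as examples.

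**4. Direct bilirubin, two readings**
- *Routine, with Note 4 as an additional reflex.* It is measured at 10 of 10 draws and the endpoint is served.
- *Reflex only.* A baseline exists only if total bilirubin exceeded 1.5 x ULN before dosing. Exclusion 26 keeps most such people out. It admits an isolated elevation with direct bilirubin below 35%, and allows one repeat. A participant could therefore have a baseline from an admitted isolated elevation, from a first screening value before a qualifying repeat, or from a Day 1 value above the trigger. Change from baseline also needs a later triggered value. In the grade summary, if the test is gradable, a triggered post-baseline value with no baseline would count against Grade 0. The two parts of the endpoint would then treat the same participant differently.

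The documents give no basis for estimating how many participants would trigger the reflex, so I give no number.

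**The case against.** **The laboratory manual may include albumin.** It may. Protocol 8.3.4 has tests done in line with a manual that is not supplied, and the endpoint lists themselves imply that someone expects the result. A reader might infer that the trial will certainly have no albumin data; the documents do not support that. What stands is narrower: the protocol's own test list omits an analyte that its endpoint names.

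**Table 9 was read from PDF by a program.** This is a fair caution. The chemistry list shows no gap or redaction mark, and its footnote numbers 1 to 5 all have a matching note. I therefore take the omission as real, subject to a look at the original page.

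**Direct bilirubin is a required parameter.** This has force. Table 9 elsewhere writes its conditions next to the test (urine microscopy, hepatitis B DNA, hepatitis C RNA, FSH and estradiol) and writes none beside direct bilirubin. Note 4 does not say that the test is done only by reflex. Appendix 5 does fractionate conditionally ("Fractionate bilirubin, if total bilirubin" reaches a threshold), and so does exclusion 26, but these govern event follow-up and eligibility, not the scheduled panel. A reader might infer that direct bilirubin is reflex only; the text shows an ambiguity and no more.

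**A reader might also infer that missing baselines simply drop out of the whole endpoint.** They do not. That holds for change from baseline, but the Grade 0 rule applies to the grade-increase part for gradable tests.

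**Conclusion.** The albumin mismatch holds. One of seven endpoint analytes is absent from the protocol's test list, and on the supplied text it is specified at 0 of 10 scheduled chemistry samples per completing participant, 8 of which are post-baseline. This assumes that Table 9 was extracted completely and that the laboratory manual does not already supply the test.

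Direct bilirubin is a request for clarification, not a demonstrated gap.

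Severity is low. The summaries are descriptive and report n, and the other five analytes are scheduled without a condition. A reader might see a hole in liver safety monitoring; there is none. The liver stopping and Hy's law criteria do not use albumin. The Note 4 trigger of 1.5 x ULN also lies below the 2 x ULN total bilirubin in the Hy's law criterion, so a direct fraction would be available there on either reading.

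**What to change.** **Albumin.** Choose one:
- Add albumin to the chemistry list in Table 9, at the draws already scheduled. This costs at most one extra result per draw, so at most 10 per completing participant. The documents give no laboratory cost, so I put no price on it.
- If the central-laboratory panel already reports albumin, correct Table 9 to say so. This is a wording change only.
- Otherwise, remove albumin from both parts of the endpoint (change from baseline and grade increase) in the Protocol synopsis, Protocol Table 3 and SAP 1.1. This is also wording only, but it gives up the analyte as an endpoint.

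**Direct bilirubin.** State in Table 9 or Note 4 whether it is measured at every scheduled chemistry draw, including baseline, or only by reflex. If it is routine, one sentence settles the matter. If it is reflex only, reconcile both parts of the endpoint: say that change from baseline is not summarised for this analyte or define how it is, and say how the Grade 0 rule in SAP 4.3.2.2 applies to participants with no baseline value.

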3.1. Primary estimand

3.1.1. Antiviral activity

- The primary objective is to evaluate the antiviral activity of orally administered VH4524184 in TN participants with HIV-1 during 10 days of monotherapy. The estimand is described by the following attributes:
- **Population:**
Overtly healthy (other than HIV-1 infection) treatment naïve individuals
- **Endpoint:**
Maximum change from baseline (Day 1) in plasma HIV-1 RNA through Day 10
- **Treatment:**
 - VH4524184 or placebo CCI [REDACTED]
- **Intercurrent events:**
 - Discontinuation of study treatment due to any reason will be addressed using **while on-treatment strategy**, i.e. any HIV-1 RNA data available after study treatment discontinuation day + 1 and prior to starting SOC will be excluded from calculation of max VLD
 - Use of SOC or other antiviral medication prior to Day 10 will be addressed using **while on-treatment strategy**, i.e., HIV-1 RNA collected after initiation of SOC, if for any reason this takes place prior to Day 10, will be excluded from calculation of max VLD
 - Use of prohibited medication will be addressed using **treatment policy strategy**, i.e., any HIV-1 RNA data available after use of prohibited medication will be used in calculation of max VLD
 - CCI [REDACTED]

• Population-level summary:

Mean of maximum change from baseline in log10 HIV-1 RNA during Days 1-10

Rationale for estimand: Interest lies in evaluating efficacy of orally administered VH4524184 CCI [REDACTED], or use of prohibited medications and not in combination with other antiretroviral medication.

3.2. Key secondary estimand(s)

3.2.1. Safety and tolerability

- The secondary objective is to assess the safety and tolerability of orally administered VH4524184. The estimand is described by the following attributes:

- **Population:**

Overtly healthy (other than HIV-1 infection) treatment naïve individuals

- **Endpoints:**

- Incidence of AEs, severity of AEs and proportion of participants who discontinue treatment due to AEs
- Change from baseline and maximum toxicity grade increase from baseline for liver panel laboratory parameter

- **Treatment:**

VH4524184 or placebo **CCI** followed by SOC on Days 10-38

- **Intercurrent events:**

- Discontinuation of study treatment due to any reason will be addressed using **treatment policy strategy**, i.e. all safety data after study treatment discontinuation will be used
- Use of SOC medication prior to Day 10 will be addressed using **while on-treatment strategy**, i.e., safety data collected after initiation of SOC, if for any reason this takes place prior to Day 10, will be excluded from monotherapy safety summaries
- Use of prohibited medication will be addressed using **treatment policy strategy**, i.e., all safety data will be used regardless of the use of prohibited medication

CCI

- **Population-level summary:**

AEs:

- Number and percentage of participants with AEs
- Number and percentage of participants with AEs by severity grade
- Number and percentage of participants with AEs leading to study treatment discontinuation

Liver panel laboratory parameters:

- Summary statistics (mean, SD, median, min, max, etc.) of change from baseline
- Number and percentage of participants with maximum toxicity grade increase relative to baseline

Rationale for estimand: Interest lies in evaluating safety and tolerability of orally administered VH4524184 irrespective of study treatment discontinuation, **CCI**, or use of prohibited medications and not in combination with other antiretroviral medication.

